**DIRECTIONS FOR FORM COMPLETION:**

1. Use this form for **all** new research project submission, and complete all sections of the form. **DO NOT REMOVE ANY OF THE TEMPLATED LANGUAGE OR MODIFY FORM.** Please be as complete and thorough as possible. Insufficient information may result in a delay in approving your project.
2. Submit this completed form along with all required supporting documents to the WBAMC Human Research Protection Office (HRPO) staff by email: [[contact]](mailto:[contact])
3. You will receive confirmation via Outlook of receipt of your new protocol package by the WBAMC HRPO.
4. Contact the DCI HRPO anytime if you need any help, or if you have questions: [contact] or [contact].

## **1. GENERAL INFORMATION SECTION**

**1.1 Protocol Title:** Prospective Study of Sleeve Gastrectomy Outcomes with Different Stapling Devices

#### **1.4 Collaborating Staff/Non-Federal Collaborators**

N/A

#### **2. ABSTRACT (Summary):**

Sleeve gastrectomy is now the most commonly performed bariatric surgery. While many studies have evaluated factors that may minimize post-operative hemorrhage and staple-line leak, we are unaware of any studies that compare outcomes between devices from the two main stapler manufacturers used in this surgery, Covidien and Ethicon. The purpose of this study is to compare intraoperative characteristics, such as time to create sleeve, intraoperative bleeding, and time needed to load each cartridge, and post-operative characteristics, such as any complication requiring readmission (leak or hemorrhage), further surgical intervention, and weight loss, between patients who underwent sleeve

gastrectomy with Covidien devices and Ethicon devices. Since we typically use the Ethicon device more frequently for this surgery due to cost, we want to test if one device is superior to another in clinical outcomes and use cost as a secondary metric. If one device has better clinical outcomes, it will be the preferred device regardless of cost. If neither proves superiority, we can justify using cost to determine which device to use in patient care.

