**5. BACKGROUND AND SIGNIFICANCE SECTION**

**5.1 Literature Review and Preliminary Data and/or Findings:**

Demonstrate that you have done a comprehensive literature search that includes the following:

**a. Date of Search:** 02 Sept 2015

**b. Search terms used:** Laparoscopic sleeve gastrectomy, stapler, bariatric surgery, Covidien, Ethicon

**c. Databases Searched:** PubMed, Google Scholar

In 2011 and 2012, it was found that 34.9% of Americans were obese . As a result, many patients will turn to bariatric surgery to assist with weight loss and resolution of obesity-related comorbidities. The three most commonly utilized bariatric procedures are the roux-en-y gastric bypass (RYGB), adjustable gastric band placement, and sleeve gastrectomy. While the RYGB was historically the most commonly performed procedure, laparoscopic sleeve gastrectomy is rapidly gaining popularity, accounting for 0.9% of bariatric procedures in academic centers in 2008 to 36.3% in 2012 . According to the American Society for Metabolic and Bariatric Surgery (ASMB), laparoscopic sleeve gastrectomy is now the most commonly performed bariatric surgery in the United States as of 2013 .

Sleeve gastrectomy was first described as part of a biliopancreatic diversion with duodenal switch in 1998 and was performed laparoscopically in 1999. It was first done as a stand-alone procedure in 2003 as part of a two-stage weight loss procedure and was recognized by the ASMBS as an acceptable option for primary bariatric surgery in 2009. The procedure is most commonly performed using a linear cutting stapler to form the gastric sleeve. The most concerning complications from this procedure include staple-line leak and hemorrhage, which occur in 2.8 and 3% of patients overall, respectively. Multiple studies have been conducted to determine how to reduce complication using staple line analogs, such as oversewing with suture, using bovine pericardium, applying liquid hemostatic matrices, and using an absorbable polymer membrane (GORE SEAMGUARD Reinforcement, W. L. Gore & Associates, Elkton, MD). In a recent study, the absorbable polymer membrane was found to have lowest leak and overall complication rate.

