### 6.3.7 Has any other Scientific Review Committee/Organization reviewed this project for scientific merit? Yes [ ] No [x]. If yes, name the organization, year, and merit/score:

#### 6.4 Statistical Consideration.

##### 6.4.1 Statistical hypothesis, primary endpoints (i.e., primary outcome variables), and secondary endpoints, if any:

Research Hypothesis: As a superiority study, the research hypothesis is Ethicon linear cutting staplers with staple line reinforcement will have different outcomes when performing laparoscopic sleeve gastrectomy when compared to Covidien staplers with staple line reinforcement.

Primary objectives: Determine if using different brand staplers affects:

1. Time of creation of sleeve from first firing to completion
2. The percent of firings with technical difficulties
3. The time for tech to load each staple cartridge (aware of Hawthorne effect. Since both arms will be subject to Hawthorne effect, the only variable should be the stapler)

Secondary objectives: Determine if using different brand staplers affects:

1. Any bleeding after creation of the sleeve (annotating whether single or multiple interventions are required)
2. Weight loss
3. Leak rates

4. Hospital readmissions or emergency room visits (For complications including but not limited to dehydration, hemorrhage, leak, internal hernia, and pain; will annotate what complication warranted readmission)
5. Further sleeve interventions

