#### **6.4.2 Data analysis:**

For the continuous primary endpoints, the two-sample t-test for 2 means will be used to compare the 2 Devices at Surgery. For the continuous secondary endpoints, such as weight loss, the General Linear Mixed Model Analysis for repeated measures over time will be used to test for the Device effect, Time effect and the Device by Time Interaction. For the binary secondary endpoints (Yes/No), such as Staple line leak, Readmission or ER visits, further sleeve interventions, over time, the General Estimating Equations (GEE) analyses will be used to test for Device effect, Time effect and the Device by Time Interaction. For all tests, the level of significance is set at 0.05.

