#### **6.4.3 Sample Size Estimation:**

75 in each arm for a total of 150 patients. The preliminary power analysis indicated 64 in each arm to be sufficient, to be able to detect a medium effect size of 0.5 for the two-sided t-test, with  $\alpha = 0.05$  and 80% power, so 11 extra patients per arm have been added for attrition. The power analysis was based on the research hypothesis of a difference in the 2 devices, with this superiority study using time to create sleeve as the primary variable.

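### A failure to prove superiority is allowed to justify choosing the stapler on cost, but with 75 per arm a null result on leak cannot show the devices are clinically interchangeable

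*Combined protocol and SAP*

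**What the plan says.** Section 2 (Abstract) sets out how the result will be used. A device with better clinical outcomes will be preferred whatever it costs. Otherwise, "If neither proves superiority, we can justify using cost to determine which device to use in patient care". The same section lists leak and hemorrhage among the outcomes to be compared.

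The rest of the plan concerns detecting a difference:

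- Section 6.4.1: "As a superiority study, the research hypothesis is Ethicon linear cutting staplers with staple line reinforcement will have different outcomes".
- Section 6.4.3 bases the sample size on a "medium effect size of 0.5 for the two-sided t-test", "with this superiority study using time to create sleeve as the primary variable". That gives 64 per arm, raised to 75 for attrition.
- Section 6.4.2 assigns GEE "For the binary secondary endpoints (Yes/No), such as Staple line leak, Readmission or ER visits, further sleeve interventions, over time", and adds: "For all tests, the level of significance is set at 0.05".
- Section 5.1 gives background rates for "staple-line leak and hemorrhage, which occur in 2.8 and 3% of patients overall, respectively".

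No section gives an equivalence or non-inferiority margin, a power statement for leak, or a commitment to report a confidence interval for the difference between devices.

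**The concern.** The Abstract makes a failed superiority test the reason for letting cost decide. That is sound only if the test would probably have found a clinically important difference had one existed, or if the interval around the estimate excludes one. The sample size was set for operative time at 0.5 SD, which says nothing about sensitivity to a complication affecting about 1 patient in 36.

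If the rule is followed as written, a null leak result could support choosing on cost while the data still allow a difference larger than the background leak rate. Nothing in the plan ensures that readers learn how large that difference could be.

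The point is limited to leak and similarly rare complications. The documents give no rates for intraoperative bleeding or for readmissions and ER visits. Weight loss is continuous, and for a 0.5 SD two-group difference the trial has reasonable power.

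**Working it through.** **Inputs.** 75 per arm, or 64 if the whole attrition allowance is used (section 6.4.3); two-sided 0.05 (sections 6.4.2 and 6.4.3); leak rate 2.8% (section 5.1).

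**1. The plan's own figure.** For d = 0.5, two-sided 0.05 and 80% power, the t-test needs 63.8, so 64 per arm; 64 + 11 = 75. This reproduces. Power at 0.5 SD is 80.1% with 64 per arm and 86.0% with 75. The sample size is correct for its own endpoint.

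**2. Expected leaks.** 75 × 0.028 = 2.1 per arm (64 × 0.028 = 1.8).

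**3. Power for leak.** I enumerated all pairs of two independent binomial counts and summed the probability of those with p ≤ 0.05 by two-sided Fisher test, or |z| > 1.96 by pooled chi-square.

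| True leak rates | 75 per arm: Fisher / chi-square | 64 per arm: Fisher / chi-square |
|---|---|---|
| 2.8% vs 5.6% (doubling) | 4.7% / 12.5% | 3.3% / 10.9% |
| 2.8% vs 11.2% (fourfold) | 40% / 55% | 31% / 48% |

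Solving for the worse-arm rate that gives 80% power at 75 per arm yields 15.0% (chi-square) or 16.8% (Fisher), more than five times the background rate. By the normal approximation, 80% power for a doubling needs 805 per arm.

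These simple tests stand in for the planned GEE. Fisher is conservative here (actual type I error 0.5% at 2.8% in both arms, against 4.1% for chi-square), so both are shown.

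**4. What a null result leaves open.** The Newcombe interval combines the Wilson limits (l, u) of each arm. With d = p2 − p1:

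- lower = d − √[(p2 − l2)² + (u1 − p1)²]
- upper = d + √[(u2 − p2)² + (p1 − l1)²]

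For 2/75 vs 7/75: p1 = 0.0267 (0.0073 to 0.0921), p2 = 0.0933 (0.0459 to 0.1803), d = 0.0667.

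- lower = 0.0667 − √(0.0474² + 0.0654²) = −0.014
- upper = 0.0667 + √(0.0870² + 0.0193²) = +0.156

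| Leaks | Difference (points) | 95% interval (points) | Fisher p | Chi-square p |
|---|---|---|---|---|
| 0/75 vs 0/75 | 0 | −4.9 to +4.9 | 1 | not defined |
| 2/75 vs 2/75 | 0 | −6.8 to +6.8 | 1 | 1 |
| 2/64 vs 2/64 | 0 | −7.9 to +7.9 | 1 | 1 |
| 2/75 vs 7/75 | 6.7 | −1.4 to +15.6 | 0.17 | 0.09 |

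With 2 leaks in one arm, significance needs 8 in the other by chi-square or 10 by Fisher.

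**5. What a formal claim would need.** The documents give no margin, so a range of 1 to 5 points is assumed for illustration. With 2.8% in both arms, one-sided 0.025 and 80% power, non-inferiority needs n = 2 × 0.028 × 0.972 × (1.96 + 0.84)² / margin² per arm: 171 at 5 points, 475 at 3, 1,069 at 2 and 4,273 at 1. Even the widest of these is more than twice the planned arm.

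**The case against.** The strongest reply is that the protocol never calls the devices equivalent or interchangeable. That is true; the word is this review's reading. The cost sentence can be taken as a default under uncertainty: both devices are approved and standard of care, and section 6.5.1 says device choice at the site is already largely financial. The sentence also appears only in the Abstract, and cost is not a listed endpoint. But it makes the null test result the justification for the choice, on clinical outcomes that include leak. A default under uncertainty should say how much uncertainty remains.

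A second reply is that GEE and mixed models yield standard errors, so intervals can be produced. That stands in part: section 6.4.2 does not forbid them, it only fails to commit to them. With so few events, however, the model may not supply one. At 2.8%, an arm has no leaks with probability 0.972^75 = 0.12, so at least one arm has none with probability 1 − 0.88² = 0.22. In that case a GEE with a logit link has no finite estimate of the device effect.

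Two cautions on the numbers also stand. The 2.8% is an overall literature rate, and reinforcement in both arms may lower it. That would narrow the interval in absolute points, but not below ±4.9 when neither arm has a leak, and it would reduce power for any given ratio. And 2 versus 7 is an illustration: if both arms truly have 2.8%, a gap of five or more leaks has probability of only about 2.7%. It shows what the rule would permit, not what is likely.

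**Conclusion.** The concern holds for leak and similarly rare complications. With about 2 expected leaks per arm, the trial would miss a doubling about 87% to 95% of the time and a fourfold rate about 45% to 60% of the time. A perfectly balanced result would still leave open a difference of 5 to 7 points, which is larger than the 2.8% background rate. Non-significance here cannot serve as evidence that the devices are clinically interchangeable.

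This rests on the 2.8% rate, on 75 evaluable patients per arm (64 is slightly worse), and on simple two-group tests in place of GEE. The sample size for sleeve creation time is not in question. The change should be made because the conclusion is meant to guide device choice in patient care.

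**What to change.** Replace the last sentence of section 2 with:

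> Non-significance will not be taken as evidence that the devices are clinically equivalent; any cost-based choice will state the largest difference in leak and other clinical outcomes that the 95% CI does not exclude.

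Add to section 6.4.2:

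> Risk differences between devices with 95% score-type (Newcombe) intervals will be reported for the binary clinical outcomes (any bleeding, leak, readmission or ER visit, further sleeve intervention).

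The single-or-multiple-intervention grading of bleeding can be tabulated alongside. The Newcombe interval remains defined when an arm has no events.

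The cost is two sentences, with no extra patients and no change to the listed primary objectives. The downside is that a null result will support a cost-based choice less strongly. This does not turn the trial into an equivalence study; that would need a justified margin and, for leak, a much larger sample.

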## **2.1 Key Words:**

Sleeve gastrectomy stapler Covidien Ethicon SEAMGUARD bariatric bleeding leak

## **2.2 Purpose:**

The purpose of this study is to perform a non-industry-funded head-to-head comparison of endoscopic linear cutting staplers made by two different manufacturers, Covidien and Ethicon Endo-Surgery, Inc.

## **2.3 Research Design:**

Prospective randomized single-blinded clinical study

## **2.4 Methodology / Technical Approach (including the number of subjects/records to be studied):**

New bariatric patients who have elected for a sleeve gastrectomy as part of standard of care will be invited to participate in the study during the bariatric clinic at William Beaumont Army Medical Center. Patients who meet the inclusion criteria will be invited to participate in the study. Please see Section 6.2.3 for specific details on study recruitment and Section 6.2.4 for specific details on the consent process. These patients will be consented in the bariatric clinic by a research resident listed on the protocol.

Three folders will be made, one for each bariatric surgeon, and 25 Covidien cards and 25 Ethicon cards will be placed into each for a total of 150 patients. All bariatric surgeons are trained and familiar with both devices. Once consented, a card will be removed at random to determine which stapler will be used. Bioabsorbable staple line reinforcement will be utilized with both staplers. Once in the operating room, the case start time, time from first staple firing to completion of sleeve, total stapler loads required, number of staple misfires, character of any staple line bleeding, and time for tech to load each cartridge will be recorded on a data collection sheet by a research resident, listed as an associative investigator on this protocol. The subject's post-operative course will follow the bariatric protocol. During follow-up, they will be monitored for weight loss, post-operative complications, and any other required interventions. This information will be obtained by reviewing the subject's medical record after follow-up appointments. Per the bariatric protocol, subjects will follow-up as noted in 6.3.5. If a patient withdraws consent for the study prior to surgery, they will still receive surgery and perioperative treatment in line with institutional protocol, and they will be withdrawn and create a vacancy for a new subject. If a patient withdraws consent after surgery, we will cease logging data for the study on that subject. We will clarify whether they want all data to be removed from the study or if they simply want no more data to be entered into the study and abide by their wishes, and they will remain in the original randomized group in accordance with intention-to-treat principles.

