### **6.2.3 Recruitment**

#### **a. Subject selection must be equitable; i.e., male/female, age range, racial and ethnic origin:**

Subjects will be selected and randomized into each group without discrimination by gender, race, or ethnicity. A predominantly female population is expected based on the historical patient population for bariatric surgery.

**b. Describe method of screening subjects and indicate when, where and how study subjects will be recruited, if applicable:**

For a bariatric patient to make it to their appointment to schedule their surgery, they will have already been screened as part of standard of care. This screening includes: ensuring BMI and comorbidities meet requirements to qualify for surgery, laboratory tests looking for an organic cause of obesity, psychiatric evaluation, upper endoscopy with gastric biopsies, ultrasound of the gallbladder if present, and several counseling sessions. Once all requirements have been met, they are seen in the bariatric clinic. Patients may choose which bariatric procedure they desire based on the information provided at the educational conferences without any coercion by staff to pick one procedure over another for research purposes. The educational conference is standardized and will not change as a result of implementation of this study. Staff may recommend the gastric bypass to certain patients based on excessive BMI or comorbidities, but the patient ultimately decides which surgery they desire based on all the information they are provided. When a patient had elected for a sleeve gastrectomy, he/she will be invited to speak with a research resident listed on the protocol, and a flyer pertaining to the project will be available for the patient to arrange a meeting to discuss the project. The research project representative will meet the patient, and details of the study will be discussed in person with patient. Pertinent topics of discussion will be that two different companies manufacture FDA-approved devices that are used for sleeve gastrectomies. Neither has been proven superior, and the aim of this study is to see if our institution has better results with one particular device in an effort to improve future patient care. The patient will be seen the day of surgery by a research representative, and he/she will be able to opt in or out at that time if they desire.

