#### **6.2.4 Consent Process**

**a. Discuss how and when subjects will be consented, who will administer consent/HIPAA authorization and steps taken to prevent coercion.**

Patients will be consented in person and sign a written consent during their bariatric pre-operative visit or at a later time if the patient so chooses. The consent process will be performed by a research physician. Patients may opt out of the study at any time. All patients will be consented individually in a private space at their convenience. Any questions related to the study will be answered prior to signing the consent form.

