**a. Describe what will happen on this study that is RESEARCH/EXPERIMENTAL:**

Subjects will be randomly assigned to one of two devices as they are scheduled for surgery using a shuffled stack of cards. Despite being the same operation that would be performed without the study, data will be collected throughout the case and recorded for research purposes as mentioned above.

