**6.3.2 Study Methodology/Procedures:**

Patients who express an interest in bariatric surgery will attend a bariatric seminar and initiate the process of scheduling bariatric surgery per department protocol. Once qualified for surgery, the patients will present to bariatric clinic, which takes place in the general surgery clinic on Tuesdays, and have a one-on-one discussion about their desired surgery with a staff physician. If the patient desires a sleeve gastrectomy, the study will be discussed. Consent will be obtained, and the patient will be randomized into the Covidien or Ethicon group. The subject will proceed with surgery per department protocol. In the operating room, a data collection sheet will be available in the operating room to make note of time for creation of sleeve from first firing to completion, total number of staple loads fired, number of misfires, character of any bleeding at the staple line and which interventions were required to control it, and time it takes for the surgical technologist to reload the stapler. At William Beaumont surgical technologists are trained on loading each linear cutting stapler by the Covidien and Ethicon representatives. We will still ensure at the start of the case they are familiar with loading the provided device. No additional training for device will be mandated, as surgical technologist turnover would make this difficult to provide equal training, and it would detract from internal and external validity, since we do not normally provide extra training. Typically the sleeve is created by staff or higher level residents (PGY-2 and above). However, all residents are trained on the devices and are therefore capable of creating the sleeve with close staff supervision, as is standard for our institution. For the purpose of this study, we intend on maintaining this practice since all level residents may be assisting and performing this surgery throughout their residency and deviation would lead to questionable internal validity. After surgery, patients will be admitted to the hospital, and care will follow the department's bariatric protocol. Once discharged, they will follow-up at 3 weeks, 6 weeks, 3 months, 6

months, and then annually. Subjects will be followed for 1 year after surgery. During that time, weight loss, presence of staple line leaks, any readmissions, and any other interventions will be monitored.

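### The stapler card is drawn before the final opt-out, and patients who withdraw between the draw and surgery are removed and replaced, so randomised patients can leave the analysed set while staff may know the arm

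*Combined protocol and SAP*

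**What the plan says.** Three places in the protocol put the draw after consent and before the operation:

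- Section 2.4: "Once consented, a card will be removed at random to determine which stapler will be used".
- Section 6.3.1(a): "Subjects will be randomly assigned to one of two devices as they are scheduled for surgery using a shuffled stack of cards".
- Section 6.3.2: "Consent will be obtained, and the patient will be randomized into the Covidien or Ethicon group", with surgery following.

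Consent is given, per section 6.2.4(a), "during their bariatric pre-operative visit or at a later time if the patient so chooses". On the day of surgery a research representative sees the patient again and, per section 6.2.3 (repeated in 6.2.4(b)), "he/she will be able to opt in or out at that time if they desire".

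Section 2.4 treats withdrawal differently on either side of the operation. Before surgery, patients leave the study and are replaced: "they will be withdrawn and create a vacancy for a new subject". After surgery, "they will remain in the original randomized group in accordance with intention-to-treat principles", although the patient may ask for all data to be removed.

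Section 2.3 describes a "Prospective randomized single-blinded clinical study" without naming the blinded party. No step hides the drawn card from the surgeon or the research resident. Section 6.4.2 defines no analysis population. Section 2.4 supplies 25 + 25 cards for each of three surgeons, 150 in all, and does not say what happens to a leaver's card.

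**The concern.** Randomisation protects the comparison only if the patients analysed are those who were randomised. Here a patient can be allocated a device, leave before the operation, and be replaced by someone else. The plan does not ask for such patients to be counted or reported by arm.

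The people around the patient in that window are not shown to be blind to the arm. The surgeon must know the device in order to operate, and the resident who times the case is in the room (6.3.4). The protocol also describes an imbalance in familiarity. Ethicon is the device used more often (2.4.1, 6.3.1(b)), and section 6.5.2 allows that less use of one device might explain minor staple-line bleeding.

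If leaving were related to both the assigned device and the expected difficulty of the case, the arms would differ at surgery for reasons other than the stapler. Sleeve creation time, the variable used for the power calculation, would be exposed to that. The unadjusted two-sample t-test in section 6.4.2 could neither detect nor correct it.

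**Working it through.** **1. The plan's own sample size.** Inputs from section 6.4.3: standardised difference 0.5, two-sided alpha 0.05, power 80%. The noncentral-t calculation gives 63.77, so 64 per arm, with power 0.8015. The stated 64 is reproduced. Adding 11 gives 75, an allowance of 11/75 = 14.7%.

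**2. Is replacement needed for power?** Power of the two-sided t-test at a difference of 0.5 SD:

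| Analysed per arm | Power |
|---|---|
| 75 | 0.8604 |
| 70 | 0.8358 |
| 67 | 0.8193 |
| 64 | 0.8015 |

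Up to 11 losses per arm leave power at or above 80%. The plan both replaces leavers and adds patients for attrition; the second already covers the need.

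**3. How large could a distortion be?** The documents give no withdrawal rate and no reasons for withdrawal, so what follows is an illustration. Assumptions:

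- a fraction d of one arm leaves selectively before surgery;
- the leavers' mean sleeve time lies m SD from that arm's mean;
- replacements pass through the same selection;
- the other arm is unaffected;
- 75 per arm are analysed.

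The mean of those who stay moves by d × m / (1 − d). With no true device difference, this is the spurious difference. The type I error is the two-sided rejection probability of a noncentral t with 148 degrees of freedom and noncentrality shift × √(75/2) = shift × 6.124.

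| d | m | Shift = d·m/(1−d) | Share of 0.5 SD | Type I error |
|---|---|---|---|---|
| 5% | 0.5 | 0.025/0.95 = 0.026 | 5% | 5.3% |
| 5% | 1.0 | 0.050/0.95 = 0.053 | 11% | 6.2% |
| 10% | 0.5 | 0.050/0.90 = 0.056 | 11% | 6.3% |
| 10% | 1.0 | 0.100/0.90 = 0.111 | 22% | 10.4% |

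If withdrawal is unrelated to arm, the expected shift is zero and the type I error stays at 5%.

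**4. The timeline table (6.3.5).** In the text copy of the table, randomisation appears under the day of surgery, but sleeve timing appears under post-operative day 1. The columns look shifted by one. If they are, randomisation belongs under the column for less than one month before surgery. The table therefore cannot settle the interval. Even a same-day draw is nowhere placed after the opt-out.

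**The case against.** The strongest reply is that the replacement rule is triggered by the patient withdrawing consent, and patients have little reason to leave because of the device. Both staplers are presented as standard care, and a patient who leaves still has the operation. Nothing gives surgeons or residents the power to withdraw anyone. This stands: the documents show that device-related loss is possible, not that it happens.

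Several stronger readings are tempting but unsupported:

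- *The draw comes weeks before surgery.* No interval is given, and consent may be later than the clinic visit.
- *Patients know their arm when they opt out.* This is not stated, and the patient may be the blinded party. Staff knowledge is itself an inference from the absence of any described concealment.
- *Section 2.4 contradicts its own intention-to-treat statement.* That statement covers withdrawal after surgery only. The gap is that no such protection applies earlier.
- *A leaver's card goes back in the folder, so the next arm is predictable.* No rule is given. A returned card drawn again at random would not reveal the arm except when few cards remain.
- *Rescheduled patients are also removed.* The documents do not say so.
- *The bias could be far larger.* Suppose the 3 to 5 slowest of 75 cases left one arm and average patients took their places. The shift would be the normal density at the upper 3/75 or 5/75 point: 0.086 to 0.129 SD, or 17% to 26% of 0.5. That requires the slowest cases to be identified exactly in advance and all to leave the same arm. If predicted and actual difficulty correlated 0.3 (an assumption), the shift would be 0.3 × 0.086 = 0.026 to 0.3 × 0.129 = 0.039 SD.

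It is also fair to say that a patient who withdraws consent before surgery may contribute no sleeve time. Keeping that patient in the randomised arm records a missing outcome; it does not recover one. This is why moving the draw does more than ending replacement alone.

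**Conclusion.** The concern holds as a design weakness. The protocol's rule removes and replaces patients who have already been randomised, during a period in which unblinded staff may know the arm, and it promises intention-to-treat handling only after surgery.

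No magnitude is established. Under the one-arm selective-loss assumptions above, the effect runs from negligible (0.03 SD, type I error 5.3%) to material (0.11 SD, 10.4%). It is nil if withdrawal is unrelated to arm. The sample size is not in question: 64 and 75 per arm are sound for the stated effect, and replacement after the draw is unnecessary up to 11 losses per arm. The change is worth making because it is cheap and closes the route, not because bias has been shown.

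**What to change.** - Draw the card on the day of surgery, after the research representative has confirmed that the patient opts in. Make sections 2.4, 6.3.1(a) and 6.3.2 and the timeline in 6.3.5 agree on this.
- Replace only patients who leave before the draw. They have not been randomised, so replacing them does no harm.
- Once drawn, a card is neither returned nor reassigned. The patient stays in the randomised arm, so the 150 cards correspond to 150 randomised patients.
- Report any withdrawal between the draw and surgery by arm, and state in section 6.4.2 that the analysis set is every patient for whom a card was drawn, with missing outcomes shown.

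The cost is a short amendment touching several sections, plus having both staplers and their reinforcement ready for each study case. Both devices are already in use at the site (6.3.1(b)), but sections 2.4.1 and 6.3.1(b) attribute the more frequent use of Ethicon to availability, so supply should be confirmed first.
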